1. STUDY OBJECTIVES/HYPOTHESIS

Primary Objective(s)

Primary aim: Compare the diagnostic yield of Magnetic Resonance Enterography (MRE) with Small-Bowel Capsule Endoscopy (SBCE) in pediatric patients with known

Inflammatory Bowel Disease (IBD) including Crohn's disease (CD) or indeterminate colitis (IC).

Secondary Objective(s)

1. To determine the detection rate of small bowel disease / complications, subjected to a strategy of Wireless Capsule Endoscopy (WCE) – small bowel screening / surveillance vs MRE in a pediatric tertiary medical institution.
2. Compare sensitivity and specificity of both MRE and WCE in identifying patients with active vs. inactive CD and IC as defined by the Pediatric Crohn's disease activity index.
3. To correlate the findings detected on WCE by Lewis score with Crohn's disease activity index.

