8. STATISTICAL CONSIDERATIONS

Measures

1. Detection rate of upper intestinal lesions in known IBD – CD undergoing WCE vs radiologic modality.
2. Definitive diagnosis of SB involvement of patients undergoing WCE vs radiologic modality in indeterminate IBD.
3. Complication rate for WCE vs 1st radiologic testing
4. Retention rate of WCE
5. The Crohn's disease activity index and its relation with the findings on both modalities
6. Lewis score on WCE

Sample size determination

With a sample size of 34 participants we will have 80% power probability to detect the 23 % difference in IBD small intestinal MRE findings and WCE detection rate similar to previously reported pediatric studies [11]. This determination uses a Chi-Square test and a two-sided significance level of 0.05. Subjects whose MRE results show findings that are contraindicated with WCE will be considered screen failures. We anticipate around 20% screen failure rate and intend to recruit 40 subjects to obtain a sample size of 34 evaluable subjects.

Data Analyses

The disease activity detection rate of MRE and WCE will be compared using McNemar's test and Chi square test. The sensitivity and specificity of both tests will be calculated based on a gold standard of classifying disease activity using Crohn's disease activity index (CDAI). The person correlation coefficient or spearman rank correlation coefficient

will be utilized to assess agreement between lewis capsule endoscopy score and CDAI. All p values will be 2 sided with statistical significance evaluated at 0.5 alpha level.

HUMAN SUBJECTS

Institutional Review Board (IRB) Review and Informed Consent

This protocol, and any subsequent modifications, will be reviewed and approved by the Pediatric IRB at The Children's Mercy Hospital & Clinics.

We request a partial Waiver of HIPAA Authorization for pre-recruitment activities.

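### Secondary objective 2 sets out to compare the sensitivity and specificity of MRE and WCE, but the analysis only calculates them: no paired difference, no interval, and an analysis set that is not fully stated

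*Combined protocol and SAP*

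**What the plan says.** Section 1, secondary objective 2: "Compare sensitivity and specificity of both MRE and WCE in identifying patients with active vs. inactive CD and IC", with activity defined by the pediatric Crohn's disease activity index.

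Section 8, Data Analyses, on the same quantities: "The sensitivity and specificity of both tests will be calculated based on a gold standard", the reference again being the activity index. Nothing further is planned for sensitivity or specificity: no difference between tests, no confidence interval, no precision or power statement.

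The only comparison between the two modalities is the sentence just before it: "The disease activity detection rate of MRE and WCE will be compared using McNemar's test and Chi square test".

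On who is analysed, section 8 treats children whose MRE findings contraindicate WCE as screen failures and says: "We anticipate around 20% screen failure rate and intend to recruit 40 subjects to obtain a sample size of 34 evaluable subjects". Sections 3 and 5 add two further ways to have an MRE but no WCE: the patency capsule does not pass, or the family withdraws once the MRE result is known.

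**The concern.** An objective to compare needs an analysis that compares. As written, objective 2 produces four percentages (sensitivity and specificity for each test) and leaves the reader to judge the gap between them unaided. Both tests are done in the same child about a week apart, so within-child pairing is the design's main asset, yet the text does not use it for this objective.

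The analysis set adds a smaller problem. If MRE were scored on every child who had one and WCE only on those who swallowed the capsule, part of any difference could reflect which children were counted. The children lost would not be a random subset, because the losses follow from failed capsule passage or from what MRE showed.

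**Working it through.** **The plan's own figure.** None is given for sensitivity or specificity. The 34 belongs to the primary comparison, which is planned at 80% power and is meant to "detect the 23 % difference in IBD small intestinal MRE findings and WCE detection rate". It cannot be settled, because neither the two rates nor the discordance is stated. For a paired test, n = ((1.96√d + 0.842√(d − 0.23²)) / 0.23)², where d is total discordance. This gives 32 at d = 0.23 (no child discordant in the reverse direction), 35 at d = 0.25 and 47 at d = 0.33. So 34 fits a paired test only with almost no reverse discordance. It says nothing about precision within the active or inactive class.

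**Does the detection-rate test stand in?** Let π be the index-active share. The overall positive rate of a test is π·Se + (1 − π)(1 − Sp). The WCE-minus-MRE difference in detection rate is therefore π·ΔSe − (1 − π)·ΔSp. At π = 0.5, a test that is 10 points better on both sensitivity and specificity shows 0.5(0.10) − 0.5(0.10) = 0. The detection rate can therefore miss a real accuracy difference, and a higher rate may mean better sensitivity, worse specificity or both.

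**Class sizes.** The active share is not in the documents. Assumption: 30%, 50% or 70%. Of 34 evaluable children this is 10.2, 17 and 23.8, so about 10–24 for sensitivity and the complement for specificity. The same shares give 12–28 of the 40 recruits in section 8 and 15–35 of the 50 in section 4.

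**One estimate.** Wilson limits are (p + z²/2n ± z√(p(1−p)/n + z²/4n²)) / (1 + z²/n). For 14/17: (0.8235 + 0.1130 ± 0.2136) / 1.2260 = 0.590 to 0.938. For 15/17 the interval is 0.657 to 0.967.

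**Two point estimates side by side.** Illustrative assumption: true sensitivities 0.90 and 0.80. With independent errors, the numbers detected are independent binomials, and the joint probabilities are summed. With fully nested errors (the better test misses nothing that the worse one finds), reversal is impossible and a tie has probability 0.90ⁿ.

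| Children in class | Worse test strictly ahead (independent) | Tie (independent) | Tie (nested; reversal 0%) |
|---|---|---|---|
| 10 | 16.5% | 21.3% | 34.9% |
| 17 | 13.9% | 14.0% | 16.7% |
| 24 | 11.5% | 10.2% | 8.0% |

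**The paired difference itself.** Approximate 95% half-width is 1.96√((d − δ²)/n), with δ = 0.10. Independent errors give d = 0.9×0.2 + 0.1×0.8 = 0.26, so half-widths of 0.31, 0.24 and 0.20 at n = 10, 17 and 24. Nested errors give d = 0.10, so 0.19, 0.14 and 0.12. In every case the half-width exceeds the assumed 10-point difference.

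**Would a test help?** Exact McNemar power at two-sided 0.05 for 90% against 70%, independent errors, is 2.0%, 13.1% and 26.0% at n = 10, 17 and 24. For a 23-point difference with 0–5% reverse discordance it is 1–3%, 18–19% and 37–49%.

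**The case against.** **Calculating both may be the comparison.** Objective 2 is secondary and unpowered, and setting the figures side by side is an ordinary reading of the word compare. This has force. A reader might infer that the sponsor will rank the tests, or declare one better, on bare point estimates. The documents do not say so, and no superiority rule is attached to this objective. What stands is that, even as description, the figures would come without intervals.

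**McNemar may be meant to cover it.** The sentence speaks of disease activity, and the next sentence ties disease activity to the same index. The scope is open to that reading. But the test is not confined to index-active children (sensitivity) or index-inactive children (specificity), so the method as stated does not supply either comparison.

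**The common set is implied.** A reader might infer that the plan has no shared analysis set. That goes too far: section 3 describes one cohort having both tests, and the screen-failure rule and the 34 evaluable subjects point to a paired set. The remaining gap is narrower. Patency-capsule failures and withdrawals after MRE are not classed, and the number expected is not given.

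**The figures can be made to look worse than they are.** Adding ties to reversals gives 22–38% under independence, but a tie is not a wrong ordering, so the two are kept apart above. Independence is also a poor fit to two tests in the same child. Positive correlation lowers the reversal rate, to zero in the nested case, although ties remain.

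**Conclusion.** The point holds in a limited form. The objective is a comparison, the analysis is a calculation, and the one comparison named is for a different quantity. The evaluable set is largely implied but not closed for patency-capsule failures and withdrawals after MRE.

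The size rests on two assumptions that the documents do not supply: a 30–70% index-active share of 34, and true sensitivities of 90% and 80% with independent errors. On these, the better test would appear worse in about 12–16% of trials and equal in a further 10–21%. The wide interval around one estimate (59–94% for 14/17) does not depend on the second assumption. Nothing here touches the primary comparison. This is a cheap improvement to a secondary objective.

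**What to change.** Replace the calculation sentence in section 8 with:

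> In children with both MRE and WCE results, sensitivity will be compared among index-active children and specificity among index-inactive children. Each estimate, and the paired difference (WCE minus MRE), will be given with a 95% confidence interval (paired-score for the difference). These comparisons are descriptive and will not be used to claim that one test is better.

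Add a line that children with MRE but no WCE will be counted and listed by reason, so that the analysis set is explicit.

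An exact McNemar p value within each class is optional and, at the power shown, adds little to the interval. If one is used, the significance level must first be reconciled. The sample-size text says "This determination uses a Chi-Square test and a two-sided significance level of 0.05", while the analysis text says "All p values will be 2 sided with statistical significance evaluated at 0.5 alpha level".

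Cost: wording only, using data already collected, with no extra children or procedures. The claim for objective 2 becomes more modest, and the results describe children who could have both tests. The calculation already promised also needs an index cut-off for active disease and a definition of a positive MRE. Section 6 gives positivity criteria only for the capsule study, and neither of the other two is stated; both are needed with or without this change.

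### The analysis plan judges every p value at a significance level of 0.5, although the trial is sized at 0.05

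*Combined protocol and SAP*

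**What the plan says.** Section 8 (Statistical Considerations) gives two significance levels.

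- **Sample size determination:** "This determination uses a Chi-Square test and a two-sided significance level of 0.05". This accompanies 34 participants, 80% power and a 23% difference between the MRE and WCE detection rates.
- **Data Analyses:** "All p values will be 2 sided with statistical significance evaluated at 0.5 alpha level". This closes the paragraph that sets out the detection-rate comparison, which "will be compared using McNemar's test and Chi square test", the sensitivity and specificity against the CDAI, and the correlation of the Lewis score with the CDAI.

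No other section gives a significance level.

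**The concern.** The two levels differ tenfold, and they do different jobs. The 0.05 describes only how 34 was obtained. The 0.5 is stated for all p values, so it is the rule by which the primary comparison and every other test would be judged.

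The Rationale says the study will help show whether capsule endoscopy is superior to MRE or complements it. Under a 0.5 rule, a claim that one modality detects more disease could rest on a difference that chance alone produces very often. The 80% power, stated at 0.05, would also not describe the analysis as written. At the least, a plan that contains both figures has not fixed its threshold in advance.

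**Working it through.** **Inputs from Section 8.** 34 evaluable subjects, each with both MRE and WCE; difference 0.23; power 80%; two-sided tests; level 0.05 for sizing and 0.5 for analysis. The documents give neither the two detection rates nor the proportion of discordant pairs (positive on one modality only). That proportion, ψ, is therefore an assumption, shown over a range.

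**1. Which level does 34 fit?** The normal-approximation sample size for McNemar's test with difference d is

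n = [z(1−α/2)·√ψ + z(0.80)·√(ψ − d²)]² / d², with d = 0.23, d² = 0.0529 and z(0.80) = 0.842.

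Take ψ = 0.24, so √ψ = 0.490 and √(0.24 − 0.0529) = 0.4326.

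- α = 0.05: (1.960 × 0.490 + 0.842 × 0.4326)² / 0.0529 = (0.960 + 0.364)² / 0.0529 = 33.1, so **34**.
- α = 0.5: (0.674 × 0.490 + 0.364)² / 0.0529 = (0.330 + 0.364)² / 0.0529 = 9.1, so **10**.

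Over ψ from about 0.23 to 0.60, α = 0.5 needs only 9 to 25 pairs. A chi-square test of two independent proportions at α = 0.5 needs 9 to 22 per group. At α = 0.05, 34 can be reached: by McNemar at ψ near 0.24, or by independent proportions near the extremes (2% versus 25%, or 75% versus 98%). The plan's 34 cannot be reproduced strictly without the missing rates, but it is compatible with 0.05 and not with 0.5.

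**2. False-positive rate at each level.** Under no true difference, the number of discordant pairs m is binomial (34, ψ). Given m, the split b versus m − b is binomial (m, ½). Summing the probability of every outcome with p ≤ α gives:

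| ψ (assumed) | Uncorrected, α = 0.5 | Uncorrected, α = 0.05 | Exact, α = 0.5 | Exact, α = 0.05 |
|---|---|---|---|---|
| 0.10 | 50.4% | 3.7% | 26.1% | 0.3% |
| 0.20 | 53.1% | 4.6% | 29.4% | 1.6% |
| 0.30 | 50.6% | 4.3% | 30.4% | 2.3% |
| 0.40 | 50.6% | 4.5% | 34.2% | 2.6% |

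The continuity-corrected test at α = 0.5 gives the same 26 to 34% as the exact test. If p must be strictly below 0.5, the exact figure at ψ = 0.10 falls to 16.5%; at ψ = 0.30 and above it barely moves.

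**3. What would count as significant at 0.5.** The critical |z| is 0.674 instead of 1.960. The uncorrected McNemar statistic is (b − c)²/(b + c) on 1 degree of freedom.

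- Split 5 versus 3: (5 − 3)²/8 = 0.50, p = 0.48. This is significant at 0.5 on a net 2 of 34 patients (5.9 percentage points). The exact p is 0.73 and the corrected p is 0.72, so those versions would not reject.
- Split 7 versus 3: (7 − 3)²/10 = 1.6, p = 0.21; exact p = 0.34. This is significant at 0.5 under either version, on a net 4 of 34 patients (11.8 points).

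**4. Lewis score and CDAI.** The critical Pearson r with 32 degrees of freedom is t/√(32 + t²).

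- α = 0.5: t = 0.682, r = 0.682/√(32 + 0.465) = **0.12**.
- α = 0.05: t = 2.037, r = 2.037/√(32 + 4.149) = **0.34**.

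**The case against.** The strongest reply is that 0.5 is plainly a slip for 0.05. The right figure stands in the same section, the sample size fits it, and the sentence just before has another typing error in the name of the correlation coefficient. On that view nobody would run the trial at 0.5, and if p values are reported any reader can apply 0.05. This is probably true as to intent. It makes the correction certain and cheap, but it does not make it unnecessary: the figure sits in the decision rule itself, and a pre-specified threshold should not have to be inferred.

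The second reply is that a 50% error rate depends on the version of the test, which the plan does not specify. That stands. About one half applies to the uncorrected McNemar test; exact and continuity-corrected versions give roughly a quarter to a third, and the 5 versus 3 example reverses under them. Each is still far above what the same version gives at 0.05.

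A third reply is that naming a single primary test and calling the other measures exploratory would go beyond this defect. That is fair; the correction of the number does not depend on it.

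**Conclusion.** The point holds. The two levels contradict each other in current text, and the one stated for the analyses is wrong as written and should be corrected before analysis. Taken literally, it raises the chance of a false-positive primary result to about 50% with the uncorrected McNemar test, or to 26 to 34% with the exact test (16% at the lowest under a strict inequality). At 0.05 the figures are about 4 to 5% and at most 2.6%. These rates assume 34 complete pairs and 10 to 40% discordance, which the documents do not give. The contradiction itself rests on no assumption.

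**What to change.** In the last sentence of Data Analyses in Section 8, replace 0.5 with 0.05 and keep the tests two-sided, so that it agrees with the sample-size paragraph. This changes one number. The 34 stays as it is, because it was already stated at 0.05, and no study procedure or data collection is affected.

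When the sentence is edited, it would help to say which version of McNemar's test will be used, since the working shows that the actual error rate depends on it. That is a clarification and not a condition of the correction.

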9. PUBLICATION OF RESEARCH FINDINGS

Results are intended to be presented at the national Gastroenterology and Inflammatory Bowel Disease conferences.

Results are intended to be published in the Gastroenterology journals.

